Approximately 30 patients are considered sufficient to explore the study objectives and will be included in this study (number of patients may be increased if there is benefit observed in initial cohort of patients. There is no formal sample size calculation estimated).

Method of assigning patient to treatment group:

All eligible patients entering into the study will be randomized in 2:1 ratio to receive the treatment A/ B respectively. A computer derived randomization schedule is planned to be generated using appropriate system e.g. SAS to assign patient to treatment groups. Randomization will be central and appropriate system (e.g. remote telephone based, computer-based email, sealed envelope) will be used to distribute randomization schedule to the site

Note: If the patient is randomised to Arm A and is not initiated itolizumab or not administer one full infusion, is then not considered randomized. The same randomisation code will be used for the subsequent subject in that particular site.

Approximate number of sites:

1-10 sites

7. Treatment

Treatment Intervention and Dose:

Arm A: Best supportive care + Itolizumab

The best supportive care to be given as per the institutions protocol will be administered

(e.g: antivirals /antibiotics/ hydroxychloroquine; oxygen therapy, etc) + **Itolizumab**

Itolizumab

Note: Premedication: Hydrocortisone 100 mg i.v (or equivalent short acting glucocorticoid) and Pheniramine 30 mg per i.v. about 30 ± 10 minutes prior to infusion.

Start at 1.6 mg/kg dose iv infusion, if well tolerated, investigator has the discretion to continue with 1.6 mg/kg dose every 2 weeks or 0.8 mg/kg weekly regimen.

Subsequent dose and frequency can be modified, deferred or stopped if patient recovers as per investigator's discretion. If patients' overall parameters improve (if performed and RT-PCR is negative) further dose need not be given. Total infusion received during study duration can vary from 1 to 4 for each patient.

Arm B: Best supportive care

The best supportive care to be given as per the institutions protocol will be administered

(e.g: antivirals/antibiotics/ hydroxychloroquine; oxygen therapy, etc)

Dosing, Handling and Storage of Itolizumab

- Itolizumab is to be stored in 6R, USP type-1, 10 mL glass vials, refrigerated condition at 2°C to 8°C and is stable at that temperature for 36 months.

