- Itolizumab is intended for use under the guidance and supervision of a physician. The diluted infusion solution should be prepared by a trained medical professional using aseptic technique; as follows:
- Calculate the dose and number of itolizumab vials needed. Itolizumab is provided as preservative-free single-use vial for IV infusion. Each vial contains 25 mg of itolizumab (5 mg/mL) in a sterile, clear, colourless, preservative-free buffer
- Itolizumab should be administered via IV infusion in 250 mL of 0.9% Sodium Chloride solution (normal saline). For this, dilute the appropriate dose of itolizumab to 250 mL with sterile normal saline. Gently mix. The total volume of the infusion will be more than 250 ml due to addition of the drug solution to 250 mL of 0.9% Sodium Chloride solution.
- Fully diluted itolizumab solution should be allowed to reach room temperature prior to infusion. Before use, the fully diluted itolizumab solution may be stored at room temperature or refrigerated at 2-8°C (36°F-46°F) protected from light. Itolizumab is stable in an infusion bag containing 250 mL of normal saline for up to 10 hours at room temperature. Do not administer as IV push or bolus.
- The infusion must be administered over a period of not less than 120 minutes and using an infusion set with an in-line, sterile, non-pyrogenic, low protein-binding filter (pore size of

1.2 µm or less). Approximately 50 mL of diluted itolizumab solution should be administered during the first hour, followed by remaining solution (more than approximately 200 mL) in the next hour. The infusion period can be extended up to 8 hours for medical reasons.

- The vials do not contain antibacterial preservatives. Therefore, any unused portion of the solution should not be stored for reuse.

Study Drug Discontinuation:

The investigator may decide to terminate the participation and discontinue further study participation of any patient. The recommended withdrawal criteria and dosing interruption criteria are presented below:

1. Protocol violation: If a protocol violation occurs that in the clinical judgment of the investigator and/or after discussion with the sponsor may invalidate the trial, the patient will be withdrawn by the investigator.
2. Consent is withdrawn: Patients have the right to withdraw from the trial at any time for any reason.

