3. Serious, life-threatening, or intolerable AEs or laboratory abnormalities in the investigator's opinion, requires withdrawal from the study for safety reasons.
4. Need arises to treat the patient with any medication that is not allowed as concomitant medication during the study; use of which, in the opinion of the investigator and/or medical monitor invalidates the study results or compromises the patient safety if continued on the study drug.
5. The investigator also withdraws a patient if the sponsor terminates the study.

8. Assessments

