## 3.2 Outcome Measures

### 3.2.1 Primary endpoint

1. Proportion of patients with deterioration of lung function as measured by\*:
  - Stable SpO2 without increasing FiO2
  - Stable PaO2 without increasing FiO2
2. Reduction of endo-tracheal intubation rate, measured as rate of patients needing intubation\*
3. Reduction in proportion of patients who need\*
  - Non-invasive ventilation
  - Invasive mechanical ventilation
  - High flow nasal oxygen
4. Time of duration of mechanical ventilation or time to end of mechanical, measured as elapsed time from the start date of mechanical ventilation to the weaning date, for patients needing intubation\*
5. One-month mortality rate between the two arms\* [ Time Frame: up to 1 month ] 1-month mortality is defined as the ratio of patients who will live after 1 month from study start out of those registered at baseline
6. Change in inflammatory markers like CRP (C-reactive protein) level, d-Dimer, ferritin etc. [ Time Frame: Arm A; baseline, during treatment (Before every dose and 12 to 24 h after every dose) up to 1 month, Arm B: baseline, 12 to 24 h and approx. 7 and 14 days after randomization ]

\* Applicable for both the arm

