## **6 General Aspects for Statistical Methods**

In general, metric variables and derived parameters will be presented using descriptive summary statistics including arithmetic mean, standard deviation, median, minimum and maximum.

Categorical variables will be presented using descriptive summary statistics including number of patients and percentages. Percentages of patients will be based on non-missing values. The presentation will be by treatment group. Individual values as well as minimum and maximum will be presented with the same number of decimal places as the raw data. Derived parameter will have as many decimal places as the measured number with the smallest number of decimal places. Descriptive statistics, such as arithmetic/geometric mean and median will be presented with an additional decimal place and standard deviation with two additional decimal places as the raw or derived data. All relevant subject data will be included in the listings; and all subjects entered into the database will be included in subject data listings. SAS 9.4 or any other validated software will be used for analysis purpose and generating Tables, Listings & Figures. P-values less than 0.05 may be reported as statistically significant.

The formatting of the final version of a table, figure, or listing may differ from what is presented in the mock shell or the presentation of the results may be changed, however the key content will remain unchanged. Additional tables, figures, and listings may be generated to supplement the planned output.

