### **13 Programming Considerations, Listing of Tables, Figures & Format, Software detail**

All tables, data listings, figures (TLFs), and statistical analyses will be generated using SAS® for Windows, Release 9.4 (SAS® Institute Inc., Cary, NC, USA) or any other validated statistical software. One SAS program will be used to create several outputs / a separate SAS program will be created for each output. Output files will be delivered in Word / pdf format.

For few assessments (weight, physical examination, vital signs haematology, biochemistry Chest X Ray/CT scan), screening assessments will be considered as baseline assessment (as day 1).

Missing data:

All attempts will be made to collect all data per protocol. Any data point that appears to be erroneous or inexplicable based on clinical judgment will be investigated as a possible outlier. If data points are identified as outliers, sensitivity analyses may be performed to examine the impact of including or excluding the outliers. Subjects who meet fatal outcome during the observing period up to 30 days will be an event. Subjects lost to follow up or withdraw consent during the observing period, will be censored at last assessment. Patient data will be censored at the time of their last observed assessment in case of lost to follow up, withdrawal consent or after 30 days of enrolment.

Following Rules may be applied for the derivation of efficacy endpoints

- Patients who discharged from hospital (with improvement, Off O2), the status at discharge will be carried forward.
- Patients who lost to follow up will be considered as Non evaluable (NE)
- Patients who worsen or met fatal outcome, status at event will be carried forward.

Note: Telephonic improvement of weaning of O2 will be considered as improved.

These rules will be applied to analyse following endpoint:

Proportion of patients with deterioration of lung function as measured by:

- Stable SpO2 without increasing FiO2
- Stable PaO2 without increasing FiO2

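### Patients the investigator withdraws have no stated Day 30 follow-up, and the SAP's non-missing denominators can then drop their outcomes from the primary comparisons

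*Protocol*

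**What the plan says.** **Withdrawal.** Protocol section 7 has a subsection headed Study Drug Discontinuation, but its opening sentence goes beyond the drug: "The investigator may decide to terminate the participation and discontinue further study participation of any patient". It then gives recommended criteria for withdrawal and for dosing interruption in one list, without marking which item is which. Item 3 covers serious, life-threatening or intolerable adverse events that the investigator thinks require leaving the study. Item 4 begins "Need arises to treat the patient with any medication that is not allowed as concomitant medication during the study". It is limited to cases where the investigator and/or medical monitor judges that the use invalidates the results, or compromises safety if study drug continues. The available text has no list of non-permitted medicines.

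**Follow-up.** Note b to the schedule in Protocol section 8.1 provides a telephone contact on Day 30 for patients who recover or are discharged early. No equivalent is written for withdrawn patients. Protocol Appendix 3 part c asks for deaths of subjects who are on the protocol. Part h ends reporting of drug-related serious events once a patient has stopped participation prematurely.

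**Analysis.** SAP section 6 states "Percentages of patients will be based on non-missing values". SAP section 13 states "Subjects lost to follow up or withdraw consent during the observing period, will be censored at last assessment". For the lung-function endpoint, section 13 adds a set of rules that it says may be applied. One makes lost patients non-evaluable ("Patients who lost to follow up will be considered as Non evaluable (NE"). The next carries forward the status of patients who worsen or die. No rule names investigator-withdrawn patients. SAP section 3.2.1, item 5, defines one-month mortality "out of those registered at baseline". Table 14.2.7 reports deaths as a count and percentage with a confidence interval and p-value, and has no rule for unknown vital status. Table 14.2.9 has a row for unknown.

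**Size.** "Approximately 30 patients are considered sufficient to explore the study objectives", allocated 2:1, and "There is no formal sample size calculation estimated".

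**The concern.** Serious adverse events and the need for additional medicines can accompany clinical decline. If a patient is withdrawn on such a ground and nobody is asked to obtain Day 30 status, a later death, intubation or step up in ventilation may go unrecorded. A non-missing denominator then removes that patient from both parts of the proportion. Follow-up outside hospital is written for patients who recover or go home, and not for those withdrawn.

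The trial is open label (SAP section 4.1) and both grounds rest on judgement. The safety limb of item 4 refers to continuing study drug, so it can apply only in Arm A. Withdrawal rates could therefore differ by arm, and any distortion need not cancel. SAP section 9 allows a p-value below 0.05 for mortality or lung function to be read as a statistically significant difference. With about 30 patients, one or two lost outcomes could decide that reading.

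**Working it through.** The plan gives no power, event rate, dropout rate or calculated sample size, so there is no figure of its own to reproduce. The check has two parts.

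**1. Trace one patient through the text.** Suppose a patient is withdrawn under item 3 or 4 and dies or is intubated before Day 30.

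- Lung function (primary outcome 1): if worsening was recorded before withdrawal, the carry-forward rule, if applied, keeps the failure. Worsening after withdrawal is not captured.
- Mortality: the endpoint definition keeps the patient in the denominator, while the general rule in SAP section 6 removes a missing value. Nothing says how an unknown counts in the numerator.
- Intubation and ventilation need: no carry-forward rule and no rule for unknown status.

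**2. Arithmetic on assumed counts.** Inputs from the documents: about 30 patients at 2:1, so 30 × 2/3 = 20 in Arm A and 30 × 1/3 = 10 in Arm B; two-sided 5% level (Protocol section 10, Statistical Analysis). The death counts are assumptions. The SAP names no test, so Fisher's exact test is my choice.

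Difference = deaths/n in Arm A minus deaths/n in Arm B.

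- Full follow-up: 2/20 − 3/10 = −20.0 points.
- One later death in Arm B lost, non-missing denominator: 2/20 − 2/9 = −12.2, a shift of 7.8.
- One later death in Arm A lost, non-missing denominator: 1/19 − 3/10 = −24.7, a shift of 4.7.
- The same losses with the baseline denominator kept but the unknown not counted as a death: 2/20 − 2/10 = −10.0, or 1/20 − 3/10 = −25.0. Fixing the denominator alone does not recover the outcome.

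With equal true proportions (6/20 v 3/10, difference 0), losing one death gives 5/19 − 3/10 = −3.7 if it is in Arm A, and 6/20 − 2/9 = +7.8 if it is in Arm B. The direction depends on which arm loses the patient.

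Fisher p-value: with D deaths in all, P(k in Arm B) = C(nB,k) × C(nA,D−k) / C(nA+nB,D), summed over tables no more probable than the one observed.

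- 1/20 v 3/10: (120 × 20 + 210)/27,405 = 2,610/27,405 = 0.095.
- The one Arm A death lost, 0/19 v 3/10: 120/3,654 = 0.033.
- 2/20 v 3/10 gives p = 0.300. With both Arm A deaths lost, 0/18 v 3/10 gives 120/3,276 = 0.037.

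Bounds: suppose 3 deaths are observed in each arm, with 2 unknown in Arm A and 1 in Arm B. The available-case difference is 3/18 − 3/9 = −16.7. The bounds are 3/20 − 4/10 = −25.0 and 5/20 − 3/10 = −5.0.

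**The case against.** There is a fair case on the other side, and several parts of it stand.

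- A reader might infer that a non-permitted medicine automatically removes a patient, or that stopping itolizumab means leaving the study. The documents do not say so. Item 4 is conditional on judgement, the list is only recommended, and it covers dosing interruption too. Protocol section 9 distinguishes discontinuing drug from withdrawal, and SAP Tables 14.1.2 and 14.3.1 record the two separately.
- For primary outcome 1, carry-forward can keep a patient who worsened before leaving as a failure. This stands, but the rule is optional, covers that endpoint only and cannot reach later events.
- Protocol Appendix 3 part g follows all serious adverse events to resolution or death, so a death after withdrawal for such an event may still be captured. It does not require Day 30 oxygen or ventilation status.
- A reader might think the censoring rule misplaced, because mortality is reported as a simple proportion. It is not: the SAP's list of graphs plans Kaplan-Meier curves for time-to-event endpoints, which censoring serves.
- The mortality definition is specific and SAP section 6 is general, so the former can be read as governing. Even so, unknown status has no numerator rule.
- Lost patients need not be the failing ones. All are hospitalised at entry, and loss after early discharge with improvement is at least as plausible.

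**Conclusion.** The gap is real and worth closing. The plan allows withdrawal from the study for reasons that can be linked to a poor course, requires no Day 30 status afterwards, and has no rule for unknown status in the mortality, intubation and ventilation proportions. Lung function is partly protected.

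The size and direction of bias cannot be derived from the documents. On the assumed counts, one lost death moves the mortality difference by 7.8 points (Arm B) or 4.7 points (Arm A) and can carry a p-value from 0.095 to 0.033. These figures rest on a 20 v 10 split, the chosen death counts, Fisher's test and a non-missing denominator.

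A reader might infer that every unevaluable patient shifts the result by 10 points in Arm B or 5 in Arm A. Those are 1/10 and 1/20, the widths that one unknown adds to best-case and worst-case bounds with fixed denominators. They are not the shift from dropping a patient.

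**What to change.** In the protocol:

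- Leave the drug-stopping criteria unchanged. Reconcile the withdrawal and dosing-interruption wording in section 7, and state that stopping itolizumab or receiving a non-permitted medicine does not end follow-up.
- Extend the Day 30 telephone contact, covering vital and oxygen status, to every patient in both arms, including those withdrawn by the investigator, unless consent to follow-up is withdrawn.

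In the SAP:

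- Use the baseline-registered denominator for mortality and for the intubation and ventilation proportions. State how it treats Arm A patients without one full infusion: Protocol section 6 and SAP section 4.5 treat them as not randomised and reuse their code, and SAP section 7 leaves them out of the ITT/FAS population.
- Make carry-forward of worsening or death mandatory, and apply it to investigator-withdrawn patients.
- Report best-case and worst-case bounds for unknown status. Counting unknown as deteriorated is a debatable imputation, so keep it as a sensitivity analysis.

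The cost is wording and a few extra calls. The call exists at present only for recovered or discharged patients, but SAP section 13 already accepts weaning from oxygen reported by telephone. The proportion stable may look less favourable.

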8.1 Schedule of Study Visits and Procedures

Visit	S1	W1	W2	W3	W4	End of Study
Weeks	-2 to 0	0	1	2	3	4 th week
Days	-14	1 [^]	8 [^]	15 [^]	22 [^]	30 [#]
Event						
Informed Consent	X					
Medical History	X					
Inclusion/Exclusion Criteria ^a	X					
Weight	X	X	X	X	X	X
Physical Examination, Vital signs ^{\$}	X	X	X	X	X	X
Hematology* [;] ^{\$}	X	X	X	X	X	X
Biochemistry** [;] ^{\$}	X	X	X	X	X	X
Chest X Ray/CT scan ##	X	X	X	X	X	
Randomisation	X					
Best Supportive Care		X	X	X	X	
Pre-medication @ in Arm A		X	X	X	X	
ALZUMAb infusion ^b		X	X	X	X	
Cytokines and Immunophenotyping assessment	X	X ^d				
PaO ₂ /FiO ₂ ratio	X	X	X	X	X	
CRP	X	X	X	X	X	X
Daily Morning SOFA Score ^c	X	X	X	X	X	
Concomitant medication check	X	X	X	X	X	X
Adverse events	X	X	X	X	X	X

[^] Window period: ± 48 Hours.

^a All inclusion / Exclusion criteria to be reviewed prior to first dosing. Screening period is up to 14 days however screening and baseline visit can happen in one day and screening assessment can be considered as baseline assessments.

^b 1.6 mg/kg dose iv infusion, if well tolerated and improvement in patient observed, investigator has the discretion to continue with 1.6 mg/kg dose every 2 weeks or 0.8 mg/kg weekly regimen in combination therapy with standard of care (anti-viral and antibiotic drugs). Subsequent dose and frequency can be modified, deferred or stopped if patient recovers as per investigator's

discretion. If patients' overall parameters improve (if performed and RT-PCR is negative) further dose need not be given. Total infusion received during study duration can vary from 1 to 4 for each patient. If patient recovers/is discharged earlier than 30 days, then patient should be contacted telephonically to get status of the patient on 30th day after enrolment.

c: Daily SOFA Scoring until patient moved out of ICU/equivalent, and later SOFA score frequency as per investigator discretion. If patient is not admitted in the ICU/equivalent at the time of enrolment, then it is recommended to capture these assessments daily for first 7 days.

Window period for assessment at 4th week or 30th day is \pm 3 days.

*Hematology assessments (blood test) include: hemoglobin, total leukocyte count, differential count, absolute neutrophil count, absolute lymphocyte count, and platelet count.

**Biochemistry assessments (blood test) include blood urea, liver function tests (i.e. serum bilirubin, AST, ALT, ALP, Serum albumin), Lipid profile (including triglyceride), LDH, serum creatinine, Procalcitonin, d-Dimer, Trop-I, Ferritin. All blood samples for hematology and biochemistry must be collected prior to dosing, and additional as per investigator discretion.

Note: Hematology and Biochemistry including (Procalcitonin, d-Dimer, Trop-I, Ferritin, LDH and CRP) are recommended every 48 to 72 hours.

§: To be recorded daily: TLC; DLC, ANC, ALC; Platelet count; S. creatinine; T. Bilirubin; morning Vitals –pulse, BP, RR; Temperature (highest temperature of the day), PaO₂/FiO₂, MAP, GCS. These daily assessments are mandatory until patient moved out of ICU/equivalent. If patient is not admitted in the ICU/equivalent at the time of enrolment, then it is recommended to capture these assessments daily for first 7 days.

@ Premedication: **In arm A:** Hydrocortisone 100 mg i.v (or equivalent short acting glucocorticoid) and Pheniramine 30 mg per i.v. about 30 \pm 10 minutes prior to infusion.

To be repeated as suggested by the investigator in ICU setting. Earlier chest X ray report may be considered after discussing with sponsor.

d: Cytokine levels in serum: such as IFN- α , TNF- α , IL-17, IL-6, IL-1, IL-4, IL-2, IL-10, GM-CSF, IFN- γ at baseline, before every dose and 12-24 h after dose in Arm A. In Arm B, same panel will be assessed at baseline, 12 to 24 h and approx. 7 and 14 days after randomization. Immunophenotyping in whole blood samples: Teff cells (CD4, CD8, Treg cells), TH17 and macrophage activated cells will be analysed at baseline, 12-24 h after 1st dose and 24h after the second/last dose in Arm A and at baseline, 12-24 h and approx. 7 days after randomization in Arm B.

Timing of administration of Itolizumab:

Patients should be randomized in the trial and given Itolizumab who are in moderate to severe ARDS as defined by PaO₂/Fio₂ ratio of < 200 or more than 25% deterioration from the immediate previous value.

OR

Baseline serum ferritin level \geq 400 ng/mL or IL-6 levels greater than 4 times ULN, if known

Note: Either of Inclusion number 6 or 7 is required for inclusion of the patient into the study. Since there is logistical delay in getting results in time, biomarker data as inclusion criteria may be used if already known.

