6. Change in inflammatory markers like CRP (C-reactive protein) level, d-Dimer, ferritin etc. [Time Frame: Arm A; baseline, during treatment (Before every dose and 12 to 24 h after every dose) up to 1 month, Arm B: baseline, 12 to 24 h and approx. 7 and 14 days after randomization]

Secondary Outcome Measures:

1. Biomarkers (IL-6, TNF-a, IL1, IL17, etc...) [Time Frame: Arm A; baseline, during treatment (Before every dose and 12 to 24 h post dose) up to 1 month, Arm B; baseline, 12 to 24 h and approx. 7 and 14 days after randomization]
2. Lymphocyte count [Time Frame: Arm A; baseline and before every dose up to 1 month, Arm B; baseline, approx. 7 and 14 days after randomization]
Lymphocyte count assessed by routinely used determination of blood count
3. PaO₂ (partial pressure of oxygen) / FiO₂ (fraction of inspired oxygen, FiO₂) ratio (or P/F ratio) [Time Frame: Arm A; baseline, during treatment (Before every dose and 48 h post dose) up to 1 month, Arm B: baseline, 48 h and approx. 7 and 14 days after randomization]
calculated from arterial blood gas analyses (values from 300 to 100)
4. Number of participants with treatment-related side effects as assessed by Common Terminology Criteria for Adverse Event (CTCAE) version 5.0 [Time Frame: during treatment and up to 30 days after the last treatment dose]*
graded according to CTCAE criteria (v5.0)
5. Radiological response [Time Frame: at baseline, after seven days and if clinically indicated (up to 1 month)]*
Thoracic CT scan or Chest XR
6. Duration of hospitalization [Time Frame: from baseline up to patient's discharge (up to 1 month)]*
Days of hospitalization and ICU
7. Remission of respiratory symptoms [Time Frame: up to 1 month]*
time to independence from non-invasive mechanical ventilation calculated in days
8. Remission of respiratory symptoms [Time Frame: up to 1 month]*
time to independence from oxygen therapy in days

* Applicable for both arms

6. Population

Patients who have tested positive for virological diagnosis of SARS-CoV2 infection (PCR) are planned to be randomised for enrolment from various centres in India.

Inclusion Criteria:

1. Male or female adults above 18 years (not tested in children yet)
2. Informed consent for participation in the study
3. Confirmed virological diagnosis of SARS-CoV2 infection (RT-PCR)
4. Hospitalized due to clinical worsening of COVID-19 infection
5. Oxygen saturation at rest in ambient air $\leq 94\%$

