## **12 Key Definitions**

For few assessments (weight, physical examination, vital signs haematology, biochemistry Chest X Ray/CT scan), screening assessments will be considered as baseline assessment (as day 1).

Stable SpO2:

- Stable SpO2: Defined as absence of increase in FiO2 to maintain Spo2 ≥ 92%
- Improvement of SpO2: Defined as decrease in FiO2 to maintain SpO2 >92%

Stable PaO2:

- Stable PaO2: Defined as up to 10% change in PaO2/FiO2 ratio from baseline
- Improvement of PaO2: Defined as > 10% improvement in PaO2/FiO2 ratio from baseline (including patients weaned off oxygen)

If assessment is missing on particular day then it should be captured from assessment available in next two days.

For lab parameters, if assessment is missing on particular day, then it should be captured from assessment available in ± 2 days.

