### 14.2.8 Change in inflammatory markers before and after dosing in Treatment ARM A

	Before dose	12-24 hrs after dosing
Serum ferritin		
First dose (n)		
Mean change		
Second dose (n)		
Mean change		
Third Dose (n)		
Mean change		
Fourth Dose (n)		
Mean change		
Programming Note: Repeat for other inflammatory markers: Serum LDH, Serum CRP, Serum d-Dimer etc		
Repeat Table for first , second, third and fourth infusion (dose) of Itolizumab		

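### Primary endpoint 6 needs marker values 12–24 h after each dose, but Protocol 8.1 does not require that draw, and the SAP's ±2-day lab rule can reach back across the dose

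*Protocol*

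**What the plan says.** Protocol section 5, Primary Outcome Measures, item 6 (repeated in SAP 3.2.1) is "Change in inflammatory markers like CRP (C-reactive protein) level, d-Dimer, ferritin etc". The Arm A time frame is baseline and "during treatment (Before every dose and 12 to 24 h after every dose) up to 1 month". The Arm B time frame is "baseline, 12 to 24 h and approx. 7 and 14 days after randomization".

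Protocol 8.1 sets the draws as follows:

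- **Ferritin and d-dimer** belong to the biochemistry panel of the double-asterisk footnote, which ends: "All blood samples for hematology and biochemistry must be collected prior to dosing, and additional as per investigator discretion".
- **CRP** is not in that panel. It has its own row, marked at screening, Days 1, 8, 15, 22 and 30, with no pre-dose or post-dose timing.
- **All three**, with LDH and others, "are recommended every 48 to 72 hours" in the note that follows.
- **The daily list** (blood counts, creatinine, bilirubin, vitals, PaO2/FiO2 and so on) contains none of the three.
- **Footnote d** does set a 12–24 h draw in both arms, but only for cytokines and immunophenotyping.

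SAP table 14.2.8 sets a before-dose column against "12-24 hrs after dosing" for ferritin, LDH, CRP and d-dimer, by dose number, in Arm A. Table 14.1.9 has 12–24 h biochemistry rows for both arms; it names ferritin and d-dimer and leaves CRP to its open-ended list. Listing 16.1.10 has a 12 h post-dose result field.

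SAP 12 adds: "For lab parameters, if assessment is missing on particular day, then it should be captured from assessment available in ± 2 days". The rule just before it, for assessments in general, looks forward only, to the next two days.

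**The concern.** The post-dose half of a primary outcome rests on a sample that the site's schedule leaves to discretion or recommendation. The protocol attaches 12–24 h timing to the cytokines, which are a secondary outcome, and not to the markers of a primary one.

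Where the sample is not taken, the fill rule comes into play. It counts in days, runs backward as well as forward, does not exclude values drawn before the dose, and does not say which of several eligible values to use. A cell labelled 12–24 h post-dose could then hold the pre-dose value or one taken two to three days later. The changes in 14.2.8 and 14.1.9, and any early comparison with Arm B, could be pulled toward zero or could describe a different interval, and nothing in the shells would show it.

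**Working it through.** The plan states no figure on this point, and the trial has no formal sample size calculation, so there is nothing to reproduce. The check is one of timing. Hours are counted from the dose, with the pre-dose draw at 0 h.

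**1. Does any draw in 8.1 fall at 12–24 h for these markers?**

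- Visit-day draws: after Day 1 the next is Day 8 with a ±48 h window, so Days 6 to 10. None is at 12–24 h.
- Recommended draws counted from the pre-dose sample: every 48 h gives 0, 48, 96 h; every 72 h gives 0, 72, 144 h. None is at 12–24 h.
- Recommended draws whose timing is unrelated to the dose (an assumption): the chance that one lands in the 12-hour target window is 12/72 = 17% to 12/48 = 25%. With about 30 patients at 2:1, Arm A has 30 × 2/3 = 20, so about 20 × 12/72 = 3.3 to 20 × 12/48 = 5 patients would have a 12–24 h value after the first dose without anyone aiming for it.

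**2. What can the ±2-day rule put in the slot?** Taking 2 days as 48 h, the window is target − 48 to target + 48.

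| Target | Window in hours | Pre-dose draw (0 h) inside? |
|---|---|---|
| 12 h | −36 to +60 | yes |
| 24 h | −24 to +72 | yes |

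By calendar day, with the dose on Day 1 and the target on Day 1 or Day 2, the windows are Days −1 to 3 and Days 0 to 4. The Day 1 pre-dose sample is inside both.

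**3. Which value would a nearest-value programmer take?** The SAP does not say nearest, so this is an illustration. The pre-dose draw is 12 to 24 h from the target. The next recommended draw is between 48 − 24 = 24 h and 72 − 12 = 60 h away. The pre-dose value is nearer in every case except a 24 h target with a 48 h draw, where the two tie.

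**4. What does the fill do to the estimate?** A pre-dose value used as its own post-dose value gives a change of 0. If a fraction f of pairs is filled that way and those pairs are otherwise typical,

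observed mean change = (1 − f) × true mean change.

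| f (assumed) | Mean change retained |
|---|---|
| 10% | 90% |
| 25% | 75% |
| 50% | 50% |

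The documents give no basis for f. A forward fill does not force a zero, but it replaces the 12–24 h change with one over as long as 60 to 72 h.

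**5. Arm B.** A rule about sampling before dosing has no meaning in that arm, and 8.1 sets no 12–24 h post-randomization draw for these markers. A baseline sample taken at randomization sits at 0 h, so step 2 applies in the same way.

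**The case against.** The best reply is that sites follow the whole protocol, not one footnote. Section 5 itself gives the 12–24 h times, and tables 14.1.9 and 14.2.8 and Listing 16.1.10 are built to receive post-dose results. The pre-dose sentence can be read as fixing when the visit sample is taken, and it does not forbid a later one. This stands: a reader might infer that the 12–24 h cells will be empty, and the documents do not show that.

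The fill rule can also be read as meant for the day-level visits (Days 7, 14, 21, 30) and not for a slot defined in hours with separate pre-dose and post-dose fields. A pre-dose value under a post-dose column heading would contradict the table's own label. This stands in part. The SAP does not direct the substitution, but the rule covers lab parameters without restriction, and its backward reach differs from the forward-only rule beside it.

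Three further inferences go too far:

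- In an open-label trial, discretion might seem to mean that investigators choose whom to bleed. Footnote d already has both arms bled at 12–24 h, so the discretion lies in which assays are added.
- Dividing 72 by 12 suggests an interval six times too long. That pairs extremes: in hours, the 12 h target's window ends at +60 h (five times) and the 24 h target's at +72 h (three times).
- The pre-dose sentence might seem to govern all three markers. It does not list CRP, although no post-dose CRP draw is required either.

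The laboratory manual promised in 8.2 could help, but it appears under biomarker sample handling, and that section refers back to 8.1 for time points.

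The stakes are also bounded. Endpoint 6 is one of six primary measures. SAP 9 summarises it descriptively, with an optional 95% CI and no named test, in about 30 patients.

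**Conclusion.** The conflict holds. Section 5 and the SAP tables need a 12–24 h value, 8.1 does not require it, and a site can comply with 8.1 without producing one. How many such values will be missing cannot be told from the documents.

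The second part holds as a permitted reading: as written, the ±2-day rule allows a pre-dose value, or one up to about 60–72 h after the dose, to stand in the 12–24 h slot. The size is conditional. The mean change shrinks by whatever share f of pairs is filled from pre-dose values, on the assumption that those pairs resemble the rest, and f is unknown. With about 20 patients in Arm A, each filled pair is about 5% of the first-dose pairs (1/20). The point merits correction because a primary outcome is affected and the remedy is small; it does not show that the endpoint is lost.

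**What to change.** 1. **Protocol 8.1.** Reconcile with section 5 by adding CRP, ferritin, d-dimer and LDH (which 14.2.8 also tabulates) to the 12–24 h draw that footnote d schedules in both arms. Limit the requirement to collect before dosing to the pre-dose sample.
2. **SAP 12.** State that the ±2-day rule does not apply to samples due 12–24 h after a dose or after randomization and never crosses a dose, so a missing post-dose value stays missing.

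The cost is one footnote amendment, one SAP sentence, a few extra local assays at a venepuncture already planned, and slightly more missing cells in table 14.2.8. The second change alone would remove the zero-change artefact but leave the gaps, so both are needed.
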